15.3 Early Death and Coagulopathy Complications in Pediatric APL

15.3.1 Specimens

Patients consenting to this biology study will have 5.4 mL of blood collected (2.7 mL into a citrate tube and 2.7 mL into a Corn Trypsin inhibitor tube) on Days 1, 8, 15 and 29 of Induction.

If any frozen citrated plasma sample is available from the day of presentation (diagnosis), it will also be analyzed for thrombomodulin levels and the CloFAL assay.

Corn Trypsin Inhibitor (CTI) tubes will be sent to each center by the central coordinating center (Children's Hospital of Michigan) upon study approval and will be replaced every 6 months (prior to the tube expiry) or if CTI tubes were used for a previous subject.

Blood will be drawn at each time point for measurement of thrombomodulin levels & for assessment of fibrinolysis by the CloFAL assay (2.7 mL citrate tube) and for thrombin generation and microparticle assay (2.7 mL Corn Trypsin inhibitor, CTI tube).

15.3.2 Preparation

Samples are to be drawn via atraumatic venipuncture. Please do not attach the CTI tube directly to the needle as it is not sterile. The tubes should be filled to ensure proper anticoagulant to blood ratio. All specimen processing should occur within 30 minutes after blood draw.

Citrate tube:

- Centrifuge at room temperature at 2500 xg for 15 minutes.
- Using a plastic disposable pipette, remove plasma, avoiding the buffy coat, and place into a plastic tube for the second spin.
- Centrifuge again using the same temperature and speed for another 15 minutes.
- Remove plasma using a clean plastic pipette, taking care to not disturb the cell button.
- Aliquot the plasma into at least 4 polypropylene tubes, 2 tubes with 500 μ L and 2 tubes with 300 μ L.
- Please clearly label with "Citrate tube" date of collection and type of sample (see [Section 15.3.3](#)).
- Please send any left over plasma in a separate tube (clearly label with "citrated plasma" and day of sample).
- Freeze samples at -80° C immediately after aliquoted into polypropylene tubes.

Corn Trypsin Inhibitor (CTI tube):

- Centrifuge at room temperature at 2400 xg for 20 minutes.
- Using a plastic disposable pipette, remove plasma, avoiding the buffy coat, and place into a plastic tube for the second spin.
- Centrifuge again at 2500 xg at room temp for another 20 minutes.

- Remove plasma using a clean plastic pipette, taking care to not disturb the cell button.
- Aliquot the plasma into at least 2 polypropylene tubes, with 1.0 mL in each tube.
- Please clearly label with “CTI tube” date of collection and type of sample (see [Section 15.3.3](#)).
- Please send any left over plasma in an additional separate polypropylene tube.
- Please clearly label with “CTI plasma” and day of sample.
- Freeze samples at -80° C immediately after aliquoted into polypropylene tubes.

15.3.3 Labeling

In addition to the study number, COG patient ID number and BPC number, clearly label “citrate” tube or “CTI” tube, date of collection and type of sample (diagnosis, Days 1, 8, 15 or 29).

15.3.5 Coagulation Studies

All patients will have local coagulation studies (including platelet count, PT, PTT, D-Dimer and fibrinogen levels) checked regularly during the first week of therapy as part of standard care to help manage any coagulopathy complications. The results of this testing will be collected on the Coagulation CRF. The study PI will

assign a score as per the International Society on Thrombosis and Haemostasis (ISTH) disseminated intravascular coagulation (DIC) score criteria.⁴⁹

16.0 NEUROCOGNITIVE OUTCOMES IN PEDIATRIC APL TREATMENT

16.1 Study Design

The purpose of this optional embedded study is to longitudinally monitor cognitive side effects from this treatment, as defined by the following endpoints:

- Primary outcome:
 - To evaluate the change in CogState scores over time, defined as a decline of 5 units in mean scores apparent at 2 years off therapy, as measured by the five tasks of the computerized CogState battery (i.e., processing speed, visual attention, visual learning, working memory, executive functioning).
- Secondary outcomes:
 - To evaluate change in parent-reported executive functioning over time, defined as a decline of 5 units in mean scores apparent at 2 years off therapy, as measured by the Behavioral Regulation, Working Memory and Metacognition Indices of the parent-completed BRIEF.
 - To evaluate change in intellectual, memory, verbal learning, and adaptive functioning over time, defined by declines on the Wechsler-derived estimated IQ and Processing Speed scores, CMS Faces and Stories memory scores, CVLT Total score, and ABAS-II General Adaptive Behavior Composite score at 4 years off-therapy.
 - To evaluate change in parent-reported psychosocial functioning and quality of life over time, defined by declines on the BASC-2 Anxiety, Depression, and Social Skills scores, and the PedsQL Total and Physical Health scores at 4 years off-therapy.

For this study, we have chosen to maximize our ability to examine neurocognitive functioning across a wide age range with minimal institutional and participant burden. Towards this aim, a combination of computerized and traditional neurocognitive measures, using two batteries that are already widely used within COG member institutions will be utilized. Specifically, we will use a brief computerized assessment system (CogState; see below) that targets the neurocognitive processes known to be most affected in leukemia survivors (i.e., attention, processing speed, and memory), and a widely used rating scale (the BRIEF, see below) to evaluate real world behaviors related to these processes.⁷⁵ In addition, participants will also complete a short neurocognitive battery that has been used in COG ALTE07C1. Specifically, participants will complete a one hour screening battery of traditional neurocognitive tests, administered by a psychologist, evaluating intellectual functioning, immediate and learning memory, processing speed, and working memory.

Both the CogState battery and the psychologist administered screening battery are being used in COG protocols. The proportion of patients who consent to the neurocognitive ancillary study embedded within COG AALL1131 is currently 71.5%. We anticipate a similar participation rate on this trial, particularly given that the neurocognitive tests used on psychologist administered battery provide a clinical screening service to the patients at no cost. The results from the screening battery can be used clinically to either establish a

need for further testing that is more likely to be covered by insurance, or shared with the child's school to help establish the need for any accommodations or other services.

The batteries have some overlap in content, but are very different in terms of their ability to detect small changes in cognitive functioning over time, and to highlight clinical meaningfulness of any demonstrated deficits. Computerized batteries allow for a larger number of responses compared with traditional measures. When tasks have a small number of items, they become susceptible to skewed distributions as well as floor and ceiling effects. With CogState, however, data from a large number of short trials is obtained, resulting in data on a true interval scale. Computerized batteries thus have the potential to be more sensitive to subtle changes in performance across time, making this an ideal tool for use in the current protocol. Finally, test-retest scores for CogState in a large sample of healthy individuals differed by approximately 2% on average, compared with between 7 - 19% for traditional measures. The absence of practice effects is of particular benefit to the current study, as it will allow us to evaluate participants across shorter intervals than are typically suggested when using traditional neurocognitive measures.

Although CogState has highly desirable psychometric properties that make it ideal for use in longitudinal studies with assessment intervals shorter than one year, traditional neuropsychological measures have well described associations with real-world functioning. Thus, in combination, the CogState and traditional task batteries will provide the ability to detect any changes in cognition over time, as well as to determine the clinical and functional significance of those changes.

CogState may be administered by bachelor's level clinical or research staff who have completed online training. These measures are already being used in 120 institutions within COG in association with an embedded, ancillary study to COG AALL1131. The test battery used in that trial is identical to the current study, and has been associated with a 96% data collection rate (aggregated across time points). The ALTE07C1 battery is currently open at 131 institutions and is associated with 90% data collection rate at time 1. Thus, there is a well-established infrastructure within COG for successfully collecting neurocognitive data in this manner.

In sum, data for this ancillary study will be obtained from two sources:

1. During treatment, data will be obtained from testing with the CogState computerized battery and the Behavior Rating Inventory of Executive Function (BRIEF) from participants aged 5 - 18 years who enroll on the ancillary neurocognitive study embedded within AAML1331.
2. At approximately the end of treatment, data will also be obtained from testing with a brief, psychologist administered battery of performance-based measures and parent questionnaires.

16.2 Eligibility Criteria for the AAML1331 Neurocognitive Study

- Enrolled on AAML1331
- ≤ 18 years at diagnosis
- English-, French- or Spanish-speaking
- No known history of neurodevelopmental disorder prior to diagnosis of APL (e.g., Down syndrome, Fragile X, William syndrome, mental retardation)

- No significant visual or motor impairment that would prevent computer use or recognition of visual test stimuli

Note: Children who are younger than age 5 years at diagnosis may enroll on the neurocognitive study, but will not be evaluated with the CogState battery until the next assessment point following their 5th birthday. Similarly, children who are younger than 30 months of age at diagnosis may enroll on the neurocognitive study but will not be evaluated with the psychologist administered battery until they reach 30 months of age.

16.3 Neurocognitive Study Consent

This correlative study is embedded within the larger therapeutic study. Consent for this study is incorporated into the consent for enrollment of eligible patients onto the parent study. Patients who enroll in AAML1331 and meet the eligibility requirements listed above may elect to enroll on this ancillary study as an option, not a requirement.

Note: Patients enrolling on this embedded study will complete assessments similar to those used on ALTE07C1 and thus patients on this study should not need to co-enroll on ALTE07C1.

16.4 Required Observations

The required observations for participants in the neurocognitive study are included in the therapy delivery maps (see [Section 4.0](#)). To reduce participant burden, all study assessments coincide with regularly scheduled clinic visits when possible.

16.4.1 Schedule of Observations

In previous literature describing neurocognitive effects in both pediatric cancer populations and in children who have been exposed to heavy metals, some changes may appear acutely (and later resolve), whereas other cognitive changes may take years to fully emerge. The assessment intervals are designed to be able to detect both acute neurocognitive changes as well as more subtle changes that would emerge over time, according to the schedule listed below.

Observation Number	Treatment Phase	CogState battery	BRIEF	Psychologist battery
1	Day 1 of Consolidation Cycle 1 (+/- 2 weeks)	✓	✓	
2	Day 1 of Consolidation Cycle 3 (+/- 2 weeks)	✓	✓	
3	End of therapy (+ 3 months)	✓	✓	✓
4	2 years Off-therapy (+/- 3 months)	✓	✓	✓
5	4 years Off-therapy (+/- 3 months)	✓	✓	✓

It is important to note that the CogState battery has not been validated in children less than 5 years of age, which means that we will be unable to capture data from computerized testing from children who are less than 5 year at diagnosis. In AAML0631, only 6 eligible participants (5%) were enrolled who were less than 5 years, so it is likely that we will have similarly few children enrolled on this trial in this age range. However, in an effort to capture information about cognitive changes in this vulnerable age group, we will attempt to collect computerized neurocognitive data (i.e., CogState) for children who are under age 5 at enrollment as soon as they turn 5 years of age. In addition, we will collect data from the performance-based measures for patients once they turn 30 months of age. Of note, the psychologist administered battery also includes standardized measurement of adaptive functioning, including developmental milestones for young patients, which may be particularly relevant in describing outcomes of interest for this age group.

16.4.2 Procedure

For each computerized assessment, participants will complete a 20 - 30 minute computerized cognitive evaluation, administered by a clinical research assistant, nurse, psychologist, or any other professional available in the pediatric oncology clinic who completes our online training in administration of CogState. While patients are completing the computerized assessment, their parent/guardian will be asked to complete a paper-and-pencil measure of executive functioning (the BRIEF, see below).⁷⁶ Completion of the BRIEF takes approximately 10 - 12 minutes.

Psychologist administered evaluations based on the ALTE07C1 battery will include abbreviated testing for intellectual functioning, memory, working memory, and verbal learning. Parents or caregivers will also be asked to complete questionnaire measures of the child's social, emotional, and behavioral functioning.

16.5 **Measures**

16.5.1 Behavior Rating Inventory of Executive Function (BRIEF)

The BRIEF is a widely used assessment of executive functioning for children aged 4 - 18 years.⁷⁶ The parent report version consists of 86 items, which map onto 2 broad areas: behavioral regulation and metacognition, as well as 2 validity scales. The Behavioral Regulation domain is further divided into 3 clinical subscales: Inhibit, Shift, and Emotional Control, whereas the Metacognition domain is divided into 5 clinical subscales: Initiate (i.e., beginning a task), Working Memory (i.e., holding information), Plan/Organize (i.e., anticipating future events and developing appropriate strategies), Organization of Materials (i.e., maintaining order in memory), and Monitor. Parents are asked to consider the frequency with which each item has been a problem over the last 6 months, responding on a 3 point Likert scale consisting of "never," "sometimes," and "often." Items were developed to be ecologically valid behavioral correlates to presumed neurocognitive difficulties with executive functioning; thus, this measure was selected to provide parent and patient reported outcomes of problems related to attention, memory, and executive function that occur in everyday life.

Psychometric properties of this measure are strong using normative samples (1,419 parents) weighted to match ethnic and gender proportions in the US population. Internal consistency is high (alpha range = 0.73 to 0.90) and test-retest reliability exceeds 0.80 for both measures over intervals from 2 to 4 weeks. Scores are linear transformations of raw scores into T scores (mean = 50, SD = 10); higher scores indicate greater difficulties.

CogState can be programmed to allow input of customized patient data at the time of testing. For this study, the CRA (or other individual administering the computerized testing) should enter each participant's COG identification number, gender, and age into the computer program. At the first evaluation, the CRA should also ask the parent or guardian accompanying the child to provide information about their highest level of education attained to estimate socioeconomic status (SES), given recent recommendations that this data be collected and included as a potential moderator of outcomes in studies of this kind. Finally, because prior longitudinal work suggests that children experiencing physical complaints at the time of testing perform more poorly on assessments both then and at subsequent evaluations, we also ask participants to report on their current experience of fatigue and nausea on a 4 point Likert scale anchored by (none/not at all and very much).

16.5.3 Psychologist administered battery

The screening battery of established neuropsychological measures as described in the ALTE07C1 protocol is being utilized. Specifically, that battery consists of an abbreviated intellectual test Block Design and Vocabulary subtests from the Wechsler Preschool and Primary Scale of Intelligence – Fourth Edition (WPPSI-IV⁷⁹; ages 30 months through 5 years), the Wechsler Intelligence Scale for Children – Fifth Edition⁸⁰ (WISC-V; ages 6 years through 16 years), or the Wechsler Adult Intelligence Scale – Fourth Edition⁸¹ (WAIS-IV; ages 17 and up). In addition, participants complete two measures of immediate visual memory (Children's Memory Scale⁸² (CMS; ages 5 through 17 years) Dot Locations and Faces, a measure of immediate verbal memory (CMS Stories subtest), and a measure of verbal learning (California Verbal Learning Test – Children's Version⁸³ for 5 years through 17 years, or California Verbal Learning Test – Second Edition⁸⁴ for 17 and up). Finally, participants complete measures of working memory (WISC-V or WAIS-IV Digit Span subtest) and processing speed (WISC-V or WAIS-IV processing speed index tasks).

The measures vary by age group and should be completed in the order presented in [Appendix VI](#).

Patient-Completed Measures

Wechsler Intelligence Scales (WPPSI-IV⁷⁹; WISC-V⁸⁰; WAIS-IV⁸¹). The Wechsler batteries measure intellectual functioning in children aged 2½ - 7 (WPPSI-IV), 6 - 16 (WISC-V), and 16+ (WAIS-IV). For this project, the Vocabulary and Block Design subtests from the version appropriate for each child's age will be used at baseline only to estimate IQ. Additionally, one working memory subtest (Digit Span) for participants age 6 years and up will be administered.

Children's Memory Scale (CMS⁸²). The CMS is a test to assess verbal and visual memory in individuals 5 - 16 years of age.

Wechsler Memory Scale, 4th edition (WMS-IV⁸⁵). The WMS-IV is a test to assess verbal and visual memory in individuals greater than 16 years of age.

California Verbal Learning Tests (CVLT-C⁸³; CVLT-II⁸⁴). The CVLT-C and CVLT-II involve verbally presenting a list learning task over the course of 5 trials. The test measures multiple aspects of how verbal learning occurs, or fails to occur, as well as the amount of verbal material learned. The CVLT-C is for individuals 5 - 16 years of age while the CVLT-II is for individuals older than 16 years of age.

Parent-Completed Measures

Behavior Assessment System for Children, 2nd edition (BASC-II⁸⁶). The BASC-II describes the behaviors, thoughts, and emotions of children and adolescents. The parent rating scale will be utilized for individuals older than 2 years and less than 18 years of age. The questionnaire yields composite and scale scores in the domains of externalizing, internalizing, school, and other problems as well as adaptive skills and behavioral symptoms.

Behavior Rating Inventory of Executive Functioning (BRIEF; BRIEF-P⁸⁷) is a parent-completed measure of behavioral executive functioning. There are two versions available: one for preschoolers (BRIEF-P) and one for older children and adolescents (BRIEF). For this study, items from the Metacognition subscales will be used. *The BRIEF will be administered at all time points as an additional outcome measure.*

Adaptive Behavior Assessment System, 2nd edition (ABAS-II⁸⁸). The ABAS-II will be used for the assessment of adaptive skills in individuals older than 2 years and less than 18 years of age. Separate scale scores are available for 10 areas of adaptive skills.

Pediatric Quality of Life Inventory Version 4 (PedsQL 4.0). The PedsQL 4.0 is a modular approach to measuring health-related quality of life in healthy children and adolescents as well as in those with acute and chronic health conditions. The Generic Version consists of 23 items, with separate parent-report forms for ages 2 - 4, 5 - 7, 8 - 12, and 13 - 18. Patients who are > 18 years of age will complete a self-report form. The questionnaire yields domain scores for Physical, Emotional, Social, and School Functioning as well as summary scores for Total Quality of Life, Physical Health, and Psychosocial Health. Reliability and validity have been established for this measure. Questions regarding the PedsQL 4.0, including question regarding access, should be sent to [name] at: [contact]

COG Language Preference Questionnaire. The 8 item COG Language Preference Questionnaire was developed to determine the primary language of study participants. Parents will complete this questionnaire for patients who are between 2 - 18 years of age. This questionnaire is available on the COG website at <https://members.childrensoncologygroup.org/Prot/AAML1331/AAML1331COGLangPrefQuest.pdf>.

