9.4.4 Study design for Study Objective 1.2.4 (Neurocognitive Outcomes)

The primary objective of this study is to use CogState testing to evaluate change in neurocognitive function from end of Induction to 2 years off therapy. The three secondary objectives include first, use of parent-reporting on the BRIEF questionnaire to assess change in neurocognitive function from end of Induction to 2 years off therapy, and for the other secondary aims, use of a psychologist administered battery to assess change in neurocognitive function from end of therapy to 4 years off therapy.

Actual CogState scores for each domain at each time point will be summarized and examined by descriptive statistics and scatter plots. Change in score for a domain from end of Induction will be calculated and similarly summarized by descriptive statistics. For the CogState scores, the mean change of score from end of Induction to a later time point will be estimated along with its 95% CI. One sample t-test on the change of score will be used to examine if there is significant decline in neurocognitive function from end of Induction to 2 years off therapy. Thus our analysis of CogState outcome data will be restricted to participants who have completed CogState testing following Induction (i.e., we will include data from patients who are 5 years of age or older by Day 1 of Consolidation Cycle 1). Outcomes for younger patients not completing the initial Induction assessment will be reported in a descriptive manner. Linear mixed models using scores from all time points as outcome will also be used to estimate the change in scores between time points with adjustment for within-patient correlation of the score by random effects for individual patients. If the change in score over time appears approximately linear in time, linear mixed models assuming time as a continuous covariate will be used to estimate the rate of decline over time and determine whether the rate of decline is significantly higher than zero.

Since each domain will be analyzed separately, the alpha level for each analysis is set to 0.01 for CogState and the psychologist administered battery and 0.017 for BRIEF according to Bonferroni adjustment to maintain an overall alpha of 0.05. For the primary objective utilizing CogState testing, assuming that there are 120 patients 5 - 18 years old who consent to participate in neurocognitive testing and receive all protocol therapy, there will be 80% power to detect the unit change

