provided in the table below in the mean change score between end of Induction and 2 years off therapy using a one-sample t-test at two-sided alpha level for the SD of the change of score between two time points provided in the table below. For the secondary objectives, mean change score will be compared from end of Induction to 2 years off therapy for the BRIEF and from end of therapy to 4 years off therapy for the psychologist administered battery, BASC-2 Anxiety, Depression, and Social Skills scores, and the PedsQL Total and Physical Health scores.

Outcome	Unit Change	Change SD
CogState (each of five tasks)	4.3	13.6
BRIEF (each of three tasks)	4.3	14.5
Estimated IQ	6.7	20.4
CVLT Total Score	4.3	13.6
Processing Speed Index	6.5	20.4
CMS Stories and Faces Immediate Memory	1.3	4.1
ABAS-II General Adaptive Composite	6.5	20.4
BASC-2 (each of three scales)	8.2	26.0
PedsQL (each of two scales)	10.3	32.4

In AAML0631, 91.7% of participants were between the ages of 5 and 18 and the upper age of enrollment was 21 years of age. Therefore, we would anticipate 91.7% or 138 of the 150 subjects in the proposed sample to be 5 - 18 years old. Based on the accrual to date to this optional embedded study, we project that up to 120 patients 5 - 18 years old will participate in neurocognitive testing and receive all protocol therapy.

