16.6 Feedback to Participants

Real-time scoring is available for the CogState measure; thus, scores for each participant may be generated immediately. CogState is not designed to be a comprehensive measure

of neurocognitive functioning; however, problems identified by CogState may indicate that the patient may require a more complete neuropsychological evaluation. Consistent with the existing protocol developed for AALL1131, we plan to inform the health care providers of participants who have scored in the bottom 7% (i.e., 1.5 SD below the mean) relative to the standardization sample for CogState, or in the most extreme 7% of scores on the BRIEF, given that extreme scores on either of these measures may reflect significant difficulties that can interfere with learning. Score reports for the BRIEF and CogState are generated automatically by the scoring programs for each measure. When children receive scores at or more extreme than 1.5 SD from the mean, their health care team will be informed of the results in the form of a letter listing the scores of concern, provided by the correlative study research team. There will not be recommendations for dose modification based on the CogState score alone, as this battery has not been validated in this manner. The health care team can follow up with families to determine if further assessment is warranted based on whether or not families are observing difficulties in their child's functioning at home or in school, and make a referral as they would normally do when families report concerns of this kind.

With regard to the psychologist administered battery, the first administration of traditional tests will be at the end of therapy and thus results will not impact individual patient treatment decisions or dose modification.

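### Section 16.5.3 restricts the IQ subtests to baseline, contradicting the planned and powered change in estimated IQ to 4 years off therapy and the battery schedule

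*Combined protocol and SAP*

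**What the plan says.** Section 16.5.3 sets the timing of the two Wechsler subtests that yield the IQ estimate: they "will be used at baseline only to estimate IQ". Section 16.6 places the start of this battery after treatment, because "the first administration of traditional tests will be at the end of therapy".

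Other parts of the document need IQ at more than one visit:

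- Section 16.1 lists a secondary outcome of change in intellectual and related functioning at 4 years off therapy, "defined by declines on the Wechsler-derived estimated IQ and Processing Speed scores" among other scores.
- Section 9.4.4 compares mean change scores "from end of therapy to 4 years off therapy for the psychologist administered battery", and its power table has a separate row for this outcome: "Estimated IQ 6.7 20.4" (detectable change, then SD of change).
- Section 2.10.4 names IQ among the domains in which decline will be measured, there at 2 years off therapy.
- Sections 7.3 and 16.4.1 schedule the psychologist battery at end of therapy, 2 years and 4 years.
- Appendix VI lists Vocabulary and Block Design for each age group (Receptive Vocabulary replaces Vocabulary in the youngest). It marks only the language questionnaire as a first-visit item.

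**The concern.** A change score needs two measurements. If the subtests are given once, the IQ change that Section 16.1 defines and Section 9.4.4 powers does not exist for that child. Section 16.5.3 names no other source for the IQ estimate: Digit Span and the processing speed tasks are separate measures.

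The restriction is hard to dismiss as loose wording. Section 16.5.3 also gives timing for another measure, placing the BRIEF at every time point, so a psychologist could reasonably read the IQ limit as a deliberate contrast. At stake is a planned test that some or all sites might be unable to supply with data. A subtest skipped at the 4-year visit, which has a window of 3 months either side, cannot be recovered later.

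**Working it through.** **Step 1: how many IQ values each instruction yields.**

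- Section 16.5.3 read literally: baseline only. The first battery is at end of therapy (Section 16.6), and the schedule has no earlier one, so end of therapy is the only visit that can serve as baseline. IQ values per child: 1. Change scores: 0.
- Schedule plus Appendix VI: end of therapy, 2 years and 4 years, with no limit on the subtests. IQ values per child: up to 3. Change scores from end of therapy to 4 years: 1.
- Sections 16.1 and 9.4.4: at least 2 values per child are required.

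Attaching the word for exclusivity in Section 16.5.3 to the purpose (estimating IQ) rather than to the visit does not remove the conflict, because the use is still placed at baseline.

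**Step 2: the plan's own power figure.** Section 9.4.4 states that "there will be 80% power to detect the unit change" shown in its table, "using a one-sample t-test at two-sided alpha level". On alpha, it says that "the alpha level for each analysis is set to 0.01 for CogState and the psychologist administered battery and 0.017 for BRIEF". The inputs for the IQ row are:

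- mean change δ = 6.7 and SD of change σ = 20.4;
- two-sided alpha 0.01;
- n = 120. This is the number stated for the CogState objective, ages 5 to 18. No separate number is given for the battery, so 120 is an assumption here.

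Power is taken from the noncentral t distribution with n − 1 degrees of freedom and noncentrality √n × δ/σ:

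- √120 × 6.7/20.4 = 10.954 × 0.3284 = 3.598.
- Power = 83.4%. The normal approximation, Φ(3.598 − 2.576) = Φ(1.022), gives 84.7%.

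The stated 80% is therefore not reproduced exactly for IQ. The change detectable with 80% power at n = 120 is 6.45. The other eight rows of the table reproduce at 79.5% to 80.7% with n = 120, so the method matches the plan's. The IQ row is slightly conservative, and this gap has no bearing on the contradiction.

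**Step 3: what the instructions do to the test.**

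| IQ pairs available | Power for a change of 6.7 |
|---|---|
| 0 (Section 16.5.3 followed everywhere) | no test possible |
| 100 | 74.3% |
| 112 | 80.2% |
| 120 (Appendix VI followed everywhere) | 83.4% |

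At least 112 pairs are needed for 80%. If 120 pairs would otherwise be available, losing more than 120 − 112 = 8 of them (8/120 = 6.7%) takes this outcome below its stated power. Losing 20 leaves 74.3%. These rows illustrate sensitivity; nothing in the documents predicts how many sites would follow which instruction.

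**The case against.** The strongest reply is that one descriptive sentence should not be taken as the operative instruction. The background (Section 2.10.4), the schedule and Appendix VI all point to repeat testing. Section 16.5.3 itself sends the reader to Appendix VI for the order of measures, and so to a list that includes the subtests without a time limit. A site working from the appendix would collect IQ at 4 years. Practice also depends on the case report forms and on the ALTE07C1 protocol from which the battery is taken, neither of which is in the documents.

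This reply stands as a limit on the consequence. A reader might infer that change in estimated IQ could not be calculated at all, or that data will be missing by site. The documents support neither. The first holds only if Section 16.5.3 overrides Appendix VI, and the second only if sites actually divide. A reader might also infer that IQ is the leading domain of concern for arsenic. Section 16.5.2 gives susceptibility to heavy metals as the reason for choosing the five CogState tasks, and IQ is one item in a longer list in Section 2.10.4.

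The reply does not remove the contradiction. No passage ranks the instructions, and a psychologist reading Section 16.5.3 has an explicit reason not to repeat the subtests.

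**Conclusion.** The point holds as an internal contradiction with conditional consequences. Section 16.5.3 gives the IQ subtests once, while Sections 16.1 and 9.4.4 need them at least twice and the schedule and Appendix VI provide for that. Followed literally, Section 16.5.3 leaves no IQ change scores. Mixed practice could leave pairs missing by site and, on the assumed 120 pairs, would bring power below 80% once more than 8 are lost.

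The scope is narrow: the estimated-IQ component of one secondary outcome, in an optional sub-study under an exploratory aim. The EFS aims, the CogState primary outcome of the sub-study, BRIEF and every other battery score are unaffected. The correction is worth making because it is nearly free and a missed 4-year assessment cannot be recovered. The conclusion about the contradiction rests on the text alone; only the power figures depend on borrowing the CogState number of 120.

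**What to change.** In Section 16.5.3, delete the words that confine Vocabulary and Block Design to baseline. State that the IQ subtests, with Receptive Vocabulary in place of Vocabulary for the youngest group, are given at end of therapy, 2 years and 4 years off therapy. Define the battery baseline as end of therapy, since no battery is scheduled before then. This brings Section 16.5.3 into line with Sections 9.4.4, 16.1 and 16.4.1 and Appendix VI. It costs a phrase and a short definition, with no visit or test beyond those already listed, and sites should be told of the clarification.

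If single testing was truly intended, keep IQ as a one-time descriptive measure instead. In that case remove estimated-IQ change from the outcomes in Section 16.1 and its row from the power table in Section 9.4.4, adjust the mention of IQ decline in Section 2.10.4, and mark the subtests in Appendix VI as first-visit items.
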